2.3 Exploratory Objective

- To correlate outcomes with blood and tumor tissue immune markers pre- and post-therapy to explore potential biomarkers of anti-tumor response

3 Investigational Plan

Subjects with advanced hepatocellular carcinoma will be enrolled in this single-arm open-label phase II study. Subjects will receive abemaciclib monotherapy 150mg twice daily for seven days then will initiate nivolumab 480mg IV every 28 days while continuing twice daily abemaciclib. Subjects will continue therapy until progression of disease, unacceptable toxicity, or withdrawal of consent.

Figure 1: Treatment Schema

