Target lesions. All measurable and/or evaluable lesions up to a maximum of 2 lesions per organ and 5 lesions in total, representative of all involved organs, should be identified as **target lesions** and recorded and measured at baseline. Target lesions should be selected on the basis of their size (lesions with the longest diameter), be representative of all involved organs, but in addition should be those that lend themselves to reproducible repeated measurements. It may be the case that, on occasion, the largest lesion does not lend itself to reproducible measurement in which circumstance the next largest lesion which can be measured reproducibly should be selected. In subjects who have received locoregional therapy to the liver, lesions that have not been treated locally should be preferentially chosen as target lesions. If a liver lesion that has been treated using locoregional therapy must be chosen as a target lesion, progression of the lesion is required after locoregional therapy. A sum of the diameters (longest for non-nodal lesions, short axis for nodal lesions) for all target lesions will be calculated and reported as the baseline sum diameters. If lymph nodes are to be included in the sum, then only the short axis is added into the sum. The baseline sum diameters will be used as reference to further characterize any objective tumor regression in the measurable dimension of the disease.

Non-target lesions. All other lesions (or sites of disease) including any measurable lesions over and above the 5 target lesions should be identified as **non-target lesions** and should also be recorded at baseline. Measurements of these lesions are not required, but the presence, absence, or in rare cases unequivocal progression of each should be noted throughout follow-up.

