8.3 Sample Size and Power Determination

Overall response rate to PD-1 therapy in HCC has varied in published studies from 15-20%. By combining available data from these studies, an overall response rate of 18% is estimated for PD-1 monotherapy. Doubling of this response rate, from 18% (H0) to at least 36% (H1) would be highly promising and worthy of additional study. With 27 subjects, a one-sided binomial test with alpha = 0.10 will have 81% power to detect an improvement in ORR from 18% (H0) to 36% (H1). For proportions, a sample of n=27 will provide 90% confidence intervals that are a maximum of 0.34 in width. For additional time to event variables, 27 subjects (21 events by 24 months) yields 90% confidence intervals for median survival that are approximately half of mean survival in width (assuming exponential survival).

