8.4 Statistical Methods

ORR and other binary variables will be analyzed using binomial exact tests, using a one-sided 10% type one error. Progression-free survival, duration of survival, and overall survival will be analyzed using Kaplan-Meier methods. PFS and DOR will be summarized as medians with 90% confidence intervals. Toxicity rates will be summarized as binomial proportions with 90% confidence intervals.

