8.4.4 Exploratory Endpoints

Analysis of Immune markers in tissue and blood will be a hypothesis-generating exploration of potential biomarkers. Logistic regression will be used to evaluate any association of response status with marker, and markers will be summarized by response status. Cox-proportional hazards regression models will be used to evaluate for any association with a marker and time to progression

9 Safety and Adverse Events

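### For tumor response, section 8.4.4 relates markers only to binary response status; adding percent change in target-lesion sum would gain power if markers track the degree of shrinkage

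*Combined protocol and SAP*

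**What the plan says.** The exploratory objective (section 2.3) is "To correlate outcomes with blood and tumor tissue immune markers pre- and post-therapy to explore potential biomarkers of anti-tumor response". Section 8.4.4 says the marker work "will be a hypothesis-generating exploration of potential biomarkers" and names two models. For response: "Logistic regression will be used to evaluate any association of response status with marker", with markers also summarized by response status. For time to progression: "Cox-proportional hazards regression models will be used to evaluate for any association with a marker and time to progression". No significance level, effect size or power is given for either.

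The continuous measure behind response is already in the plan. Section 7.10.3 has the target-lesion diameters summed at baseline and adds: "The baseline sum diameters will be used as reference to further characterize any objective tumor regression in the measurable dimension of the disease". Section 7.10.5.1 defines partial response as a fall of at least 30% in that sum from baseline, and progression by a rise from the smallest sum on study. Follow-up sums are therefore needed at each scan. No section analyses percent change as an outcome.

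**The concern.** Cutting percent change at 30% discards information. A subject with 29% shrinkage is grouped with one whose lesions grew by 19%, and 31% shrinkage counts the same as 90%. The cut is needed for the primary ORR, which is compared with a historical rate of 18%. The marker analysis has no historical comparator, so nothing forces the cut there.

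At stake is the chance of noticing a marker that is truly related to shrinkage. With few responders, the yes/no analysis can miss such a marker where a full-scale analysis of the same scans would more often find it. The Cox models address a different outcome and do not measure depth of response. A penalized or exact logistic model would steady the odds ratio but would still use only yes or no.

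**Working it through.** **Inputs from the documents.** n = 27 and response rates of 18% (H0) and 36% (H1), section 8.3; partial response at a 30% decrease, section 7.10.5.1; 21 events by 24 months for time-to-event variables, section 8.3.

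**Inputs assumed.** The correlation rho between marker and shrinkage, the shape of the relation, and the two-sided 5% level. The only stated level nearby is for ORR and other binary variables: "ORR and other binary variables will be analyzed using binomial exact tests, using a one-sided 10% type one error".

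**Step 1: the plan's own figure.** Section 8.3 states: "With 27 subjects, a one-sided binomial test with alpha = 0.10 will have 81% power". Rejecting at 8 or more responses of 27 gives
- P(X ≥ 8 | 27, 0.18) = 0.0977
- P(X ≥ 8 | 27, 0.36) = 0.812

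The 81% reproduces. It concerns the primary test only.

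**Step 2: responders available to the logistic model.** 27 × 0.18 = 4.9 and 27 × 0.36 = 9.7, so about 5 to 10.

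**Step 3: graded relation.** Draw marker x ~ N(0,1) and shrinkage z = rho·x + √(1 − rho²)·e with e ~ N(0,1). Call the subject a responder if z exceeds the quantile that gives the stated ORR. Compare the logistic likelihood-ratio test of response on x with the Spearman test of z on x (4,000 replicates, n = 27, two-sided 5%).

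| ORR | rho | Logistic | Spearman | Gap (points) |
|---|---|---|---|---|
| 36% | 0.3 | 24% | 30% | 6 |
| 36% | 0.4 | 40% | 51% | 11 |
| 36% | 0.5 | 59% | 72% | 13 |
| 18% | 0.3 | 21% | 31% | 10 |
| 18% | 0.4 | 32% | 49% | 17 |
| 18% | 0.5 | 48% | 73% | 25 |

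Repeat runs move these by about a point, which gives roughly 5 to 14 points at ORR 36% and 10 to 25 at ORR 18%. At rho = 0 the logistic test rejects about 6% and Spearman about 5%, so the gain is not bought with false positives.

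**Step 4: other levels and sizes (rho = 0.5).**
- Two-sided 20%, equivalent to one-sided 10%: 82% vs 89% at ORR 36% (7 points) and 73% vs 90% at ORR 18% (17 points).
- n = 20 at the 5% level: 46% vs 57% and 37% vs 57%. The value 20 is an assumption; section 7.11.2 lets biopsies be omitted, so tissue markers may have fewer than 27 subjects.

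**Step 5: a relation of a different shape.** Let the marker mean be 1 SD higher in responders, with depth inside each class unrelated to the marker (also an assumption). At the 5% level logistic regression now wins: 68% vs 44% at ORR 36%, and 50% vs 20% at ORR 18%.

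**Step 6: the Cox model.** If time to progression were as strongly related to the marker as percent change is (a favorable assumption), with 21 of 27 events and the 5% level, Cox power against linear regression on percent change is 49% vs 54% at rho 0.4 and 71% vs 78% at rho 0.5.

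**The case against.** The strongest case against has four parts.

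- **Markers are not tied to binary status alone.** A reader might infer from the response model that the whole marker analysis rests on a yes/no outcome. Section 8.4.4 does not support that: the Cox models use time to progression, and Step 6 shows they can come close to the continuous analysis. The loss belongs to the response model only.
- **The size is not a documented figure.** A reader might quote a flat loss of about 15 to 24 points. One set of runs gives that for rho = 0.5 with normal residuals (73 − 58 = 15 at ORR 36%; 72 − 48 = 24 at ORR 18%). Other assumptions give smaller or larger gaps, and the documents fix neither rho nor the level.
- **The simulation in Step 3 favors the continuous analysis by construction.** It makes response a cut of a variable linearly related to the marker. Step 5 shows the sign can change. This stands, and it is the main reason not to replace the logistic model.
- **Response status is the trial's primary endpoint.** Reducing it to a description in the marker analysis would drop inference on that endpoint. Best percent change also ignores new and non-target lesions, so a subject who progresses by a new lesion while target lesions shrink ranks as favorable. This stands too.

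The analysis is also declared hypothesis-generating, and nothing bars a supplementary percent-change analysis. That limits the consequence. It does not remove the benefit of prespecifying the analysis, which avoids choosing the response scale after seeing the data.

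**Conclusion.** The point holds for the tumor-response model alone. Percent change in target-lesion sum can be derived from planned scans, is not analysed, and would be the more powerful scale if markers track the degree of shrinkage: about 5 to 14 points at ORR 36% and 10 to 25 points at ORR 18%. Those ranges assume n = 27 with complete data, a bivariate normal relation with rho 0.3 to 0.5, a two-sided 5% level, likelihood-ratio logistic regression against Spearman, and response set by percent change alone. If the marker only separates responders from non-responders, the binary model is better. Since the plan cannot know which applies, the case is for having both analyses. No primary or secondary endpoint is affected, so the priority is low.

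**What to change.** In section 8.4.4, add one prespecified analysis: the Spearman correlation (or a linear regression) of each marker with best percent change from baseline in the sum of target-lesion diameters, using scans up to first RECIST 1.1 progression, reported with a 90% confidence interval. Keep the logistic regression, the summaries by response status and the Cox models as they are.

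The cost is a sentence of plan wording and a few lines of code, with no new scans, samples or subjects. There are two small downsides. Each marker gains one more exploratory test, and percent change misses new and non-target lesions, which the retained analyses cover.

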9.1 Definitions

9.1.1 Unanticipated Problems Involving Risk to Subjects or others

Any incident, experience, or outcome that meets all of the following criteria:

- Unexpected in nature, severity, or frequency (i.e. not described in study-related documents such as the IRB-approved protocol or consent form, the investigators brochure, etc.)
- Related or possibly related to participation in the research (i.e. possibly related means there is a reasonable possibility that the incident experience, or outcome may have been caused by the procedures involved in the research)
- Suggests that the research places subjects or others at greater risk of harm (including physical, psychological, economic, or social harm).

9.1.2 Adverse Event

An **adverse event** (AE) is any symptom, sign, illness or experience that develops or worsens in severity during the course of the study. Intercurrent illnesses or injuries should be regarded as adverse events. Abnormal results of diagnostic procedures are considered to be adverse events if the abnormality:

- results in study withdrawal
- is associated with a serious adverse event
- is associated with clinical signs or symptoms
- leads to additional treatment or to further diagnostic tests
- is considered by the investigator to be of clinical significance

9.1.3 Adverse Events of Special Interest

AESIs (serious or non-serious) are defined as AEs of scientific and medical concern specific to the investigational product or program, for which ongoing monitoring and rapid communication by the Principal Investigator to drug manufacturer can be appropriate. Such an event might warrant further investigation in order to characterize and understand it. Depending on the nature of the event, rapid communication by the Principal Investigator to other parties (e.g., regulators) might also be warranted.

Details on currently agreed list of AESIs for abemaciclib can be found in the current IB. These AESIs are to be reported to Eli Lilly expeditiously within 1 business day of knowledge of the event, during the study through 30 days after receiving the last dose of study treatment, according to the procedures below

9.1.4 Serious Adverse Event

Serious Adverse Event

Adverse events are classified as serious or non-serious. A **serious adverse event** is any AE that is:

- fatal
- life-threatening
- requires or prolongs hospital stay
- results in persistent or significant disability or incapacity

CONFIDENTIAL

- a congenital anomaly or birth defect
- an important medical event

Important medical events are those that may not be immediately life-threatening, but are clearly of major clinical significance. They may jeopardize the subject and may require intervention to prevent one of the other serious outcomes noted above. For example, drug overdose or abuse, a seizure that did not result in in-patient hospitalization, or intensive treatment of bronchospasm in an emergency department would typically be considered serious.

All adverse events that do not meet any of the criteria for serious should be regarded as **non-serious adverse events**.

Any AE that results in hospitalization or prolonged hospitalization should be documented and reported as an SAE unless specifically instructed otherwise in this protocol. Any condition responsible for surgery should be documented as an AE if the condition meets the criteria for an AE.

Neither the condition, hospitalization, prolonged hospitalization, nor surgery are reported as an AE in the following circumstances:

- Hospitalization or prolonged hospitalization for diagnostic or elective surgical procedures for a preexisting condition. Surgery should not be reported as an outcome of an AE if the purpose of the surgery was elective or diagnostic and the outcome was uneventful.
- Hospitalization or prolonged hospitalization required to allow efficacy measurement for the study.
- Hospitalization or prolonged hospitalization for therapy of the target disease of the study, unless it is a worsening or increase in frequency of hospital admissions as judged by the clinical investigator.

Events of progression of the subject's underlying cancer as well as events clearly related to progression of the subject's cancer (signs and symptoms of progression) should not be reported as a serious adverse event unless the outcome is fatal within the safety reporting period. If the event has a fatal outcome within the safety reporting period, then the event of Progression of Disease must be recorded as an AE and as a SAE with CTC Grade 5 (fatal outcome) indicated.

Preexisting Condition

A preexisting condition is one that is present at the start of the study. A preexisting condition should be recorded as an AE if the frequency, intensity, or the character of the condition worsens during the study period.

General Physical Examination Finding

At screening, any clinically significant abnormality should be recorded as a preexisting condition. At the end of the study, any new clinically significant findings/abnormalities that meet the definition of an AE must also be recorded and documented as an AE.

Abnormal Laboratory Values

An abnormal laboratory value that is not already associated with an AE is to be recorded as an AE only if any one of the following criteria is met:

- an action on the study drug is made as a result of the abnormality
- intervention for management of the abnormality is required
- at the discretion of the investigator should the abnormality be deemed clinically significant

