7.10.6 Toxicity Evaluation

All subjects entered into the study and who are given at least one dose of abemaciclib will have detailed information collected on adverse events for the overall study safety analysis. All adverse events will be categorized and tabulated using CTCAE v. 5.0.

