8.2 Secondary Endpoints

1. Toxicity rates is an ordinal measure, graded using CTCAE v. 5.0, or dichotomized (binary).
2. Overall response rate using iRECIST criteria (binary)
3. Progression-free survival (time to event)
4. Duration of response (time to event)
5. Overall survival (time to event)

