8.4.3 Safety Analysis

All subjects entered into the study and who are given at least one dose of abemaciclib will have detailed information collected on adverse events for the overall study safety analysis. All adverse events will be categorized by CTCAE v. 5.0, tabulated as ordinal, and summarized as binomial proportions.

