9.2 Adverse Event Reporting Period

The study period during which adverse events must be reported is normally defined as the period from the initiation of any study procedures to the end of the study treatment follow-up. For this study, the study treatment follow-up is defined as 30 days following the last administration of study treatment.

CONFIDENTIAL

This material is the property of the University of Pennsylvania.

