9.4 Relationship of AE to Study

The relationship of each adverse event to the study procedures should be characterized by the Investigator as definitely related, probably related, possibly related, unlikely or unrelated to study therapy.

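### Toxicity rates use all adverse events without attribution, so progression deaths up to 30 days after last treatment, recorded as Grade 5 AEs, count in any overall Grade 5 or high-grade rate

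*Combined protocol and SAP*

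**What the plan says.** Toxicity is a secondary objective (2.2, by category) and a secondary endpoint (3.4.2 and 8.2). It is graded by CTCAE v. 5.0, either as an ordinal measure or dichotomised. No cut-off is given and relatedness is not mentioned.

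Three places describe the analysis:

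- 7.10.6: "All adverse events will be categorized and tabulated using CTCAE v. 5.0".
- 8.4: "Toxicity rates will be summarized as binomial proportions with 90% confidence intervals".
- 8.4.3: "All adverse events will be categorized by CTCAE v. 5.0, tabulated as ordinal, and summarized as binomial proportions".

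The safety set is everyone given at least one dose of abemaciclib (7.10.6, 8.4.3).

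Section 9.1.4 deals with progression. Progression, and events clearly due to it, "should not be reported as a serious adverse event unless the outcome is fatal within the safety reporting period". In that fatal case, "the event of Progression of Disease must be recorded as an AE and as a SAE with CTC Grade 5 (fatal outcome) indicated". On the length of the period, 9.2 states that "the study treatment follow-up is defined as 30 days following the last administration of study treatment".

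Section 9.4 has the investigator classify each event as "definitely related, probably related, possibly related, unlikely or unrelated to study therapy". Section 8 does not use that classification.

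**The concern.** Each rule is ordinary on its own. Recording an in-window progression death as a Grade 5 SAE is a safety-reporting convention, and tabulating all-cause events is a legitimate choice. The problem is the combination under the name of toxicity rates. A death from HCC soon after the last dose enters the same proportion as a death caused by treatment, and the statistical plan provides no second table to tell them apart.

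In a randomised trial the control arm would show the background rate. This trial has none. The Introduction puts median survival in advanced HCC at less than one year, and 4.1 admits Child-Pugh scores up to 7, so some deaths within 30 days of the last dose are plausible. Section 1.1 assumes, rather than shows, that the combination is tolerable in HCC, and 1.4 rests the abemaciclib dose on breast-cancer data with a different PD-1 inhibitor. The toxicity endpoint is the trial's own check on that assumption. The missing attribution rule affects lower grades too, because background liver-related events enter the rates in the same way.

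**Working it through.** **1. Tracing an event through the text.** A subject progresses, stops treatment and dies of HCC 20 days after the last dose.

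- 9.2: day 20 is inside the 30-day window.
- 9.1.4: the event is therefore recorded as an AE and SAE, Grade 5.
- 9.4: the investigator would presumably classify it as unlikely or unrelated.
- 7.10.6 and 8.4.3: all AEs are tabulated, so this one is included. No rule in section 8 drops it or shows it apart.
- 9.6: the monitoring committee's exception for progression covers Grade 3 or 4 events and concerns reporting. It does not reach Grade 5 or the analysis table.

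Had the same subject died on day 45, 9.1.4 would not apply and the death would count only for survival.

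**2. The plan's own precision figure.** Section 8.3 states that 90% intervals for a proportion with n = 27 are at most 0.34 wide. The exact (Clopper-Pearson) interval for x events has limits

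- lower = Beta quantile (0.05; x, n − x + 1), or 0 if x = 0
- upper = Beta quantile (0.95; x + 1, n − x)

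Its greatest width for n = 27 is 0.340, at x = 13, which reproduces the stated figure. The Wald and Wilson maxima are 0.317 and 0.302. Exact intervals are therefore used below.

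**3. Effect on the Grade 5 proportion.** The documents give no rate of progression death within 30 days of last treatment, so the counts are assumptions. Take 27 treated subjects and no treatment-related death. The related Grade 5 rate is 0/27 = 0%, with upper limit 1 − 0.05^(1/27) = 10.5%. Under the all-AE rule each in-window progression death adds 1/27 = 3.7 percentage points:

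| In-window progression deaths | Grade 5 rate | Exact 90% CI |
|---|---|---|
| 0 | 0% | 0-10.5% |
| 1 | 3.7% | 0.2-16.4% |
| 2 | 7.4% | 1.3-21.5% |
| 4 | 14.8% | 5.2-30.8% |

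A dichotomised rate such as Grade 3 or higher moves less. A progression death raises it only if that subject had no other event of that grade.

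**4. How likely is at least one?** If each subject has probability q of such a death, the expected number is 27q and the chance of at least one is 1 − (1 − q)^27. For assumed q of 5%, 10% and 20%, the expected numbers are 1.35, 2.7 and 5.4, and the chances are 75%, 94% and 99.8%.

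**5. Denominator.** Twenty-seven is the number evaluable for efficacy (4.4, 7.10.2). Under 8.4.2 subjects who are not evaluable are replaced, yet anyone given abemaciclib stays in the safety set. A subject who dies of progression before re-imaging is therefore replaced but still counted for safety. With an assumed 32 treated, 2 to 4 deaths give 2/32 = 6.3% to 4/32 = 12.5%.

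**The case against.** The case on the other side has real force.

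- **Presentation.** Section 2.2 asks for toxicity by category, and 9.1.4 records the event under its own name. A by-category table could show progression as its own row, visibly apart from drug effects. The distortion arises only when terms are collapsed into one Grade 5 or high-grade proportion, and the plan gives no cut-off. This stands, and it is why the point is limited to such collapsed rates. But nothing requires the separate row or keeps progression out of a collapsed rate.
- **Attribution is on file.** It is recorded for each event (9.4), and reports to the manufacturer need it at the outset (9.5.2). An independent clinician reviews SAEs at least every 6 months (11.1). A reader might infer that the plan could conceal a treatment-related death. The documents do not support that, because such a death would be identifiable. What is missing is an analysis that uses the attribution. Choosing one after the data of an open-label single-arm trial are known is weaker than naming it now.
- **Attribution is fallible.** Investigators are unblinded, both drugs have hepatotoxicity rules (3.1.1, 3.2), and the tumour is in the liver. A related-only endpoint, or an all-cause table without progression deaths, could lose a hepatic drug death labelled as progression. This stands and shapes the fix.
- **Little hangs on the number.** No toxicity threshold, null rate or numerical stopping boundary uses it, and the primary response test is untouched. This also stands.

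**Conclusion.** The point holds in a limited form. As written, progression that is fatal by 30 days after last treatment counts in any overall Grade 5 or dichotomised high-grade toxicity proportion. Section 8 contains no treatment-related analysis to set beside it.

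A reader might go further and infer that HCC deaths in general will be reported as Grade 5 toxicity of the combination. The documents do not support that. Deaths after the window, during follow-up of up to 24 months (6.2.5), fall outside the rule, and no section attributes the in-window deaths to the drugs. The risk comes from an all-cause table that carries the name toxicity.

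The size is 3.7 percentage points per such death if 27 are treated, and somewhat less if more are. The number of deaths is assumed throughout. The matter concerns a secondary endpoint and what the trial can conclude about tolerability. It does not affect the primary test or any decision rule. It is worth correcting because the correction is cheap and the data are already collected.

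**What to change.** In 8.4.3, and by cross-reference in 7.10.6 and 8.4:

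1. Tabulate worst CTCAE grade per subject twice: once for all-cause events, and once for events rated possibly, probably or definitely related under 9.4, with relation to either drug sufficient. Give 90% confidence intervals for both, with all subjects given at least one dose of abemaciclib as the denominator.
2. Keep fatal progression in the all-cause table as a separately identified line, and give the Grade 5 proportion with and without it.

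The all-cause table must stay complete. The related rates depend on unblinded investigator attribution, and a complete table lets a reader look for a misattributed death.

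The cost is a few lines of analysis text and one extra table. No new data are needed, and the recording and reporting of these deaths under section 9 do not change.
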